7. MULTIPLE COMPARISONS AND MULTIPLICITY

No multiplicity control will be applied to the efficacy analysis or other endpoints.

8. SAFETY ANALYSIS

8.1. General

Safety analyses will be performed on the ITT analysis set, unless otherwise noted. Summaries will be presented by overall patients. Selected safety data might also be presented by age group, as applicable.

For continuous variables, descriptive statistics will be provided for actual values and changes from baseline to each time point. For categorical variables, patient counts and percentages will be provided.

Summaries of potentially clinically significant abnormal values will include all post-baseline values (including scheduled, unscheduled, and early termination visits).

Safety assessments and time points are provided in [Table 3](#).

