#### 9.6. Safety Endpoints and Analysis

The primary objective of this study is to evaluate the safety and tolerability of long-term therapy with TEV-50717 in children and adolescents with DCP.

The safety measures/endpoints are as follows:

- adverse events
- vital signs
- children's C-SSRS
- ECG parameters
- clinical laboratory parameters (hematology, serum chemistry, and urinalysis)
- ESRS (subscale I and II)
- CBCL
- ESS

Safety analyses will be presented for the ITT analysis set (Section 9.2.1). Patients who did not receive any TEV-50717 will be excluded from the summaries and presented in listings only.

All adverse events will be coded using the Medical Dictionary for Regulatory Activities (MedDRA). Each patient will be counted only once in each preferred term or system organ class (SOC) category for the analyses of safety. Summaries will be presented for all adverse events (overall and by severity), adverse events determined by the investigator to be related to TEV-50717 (ie, reasonable possibility; see Section 7.1.4) (defined as related or with missing relationship) (overall and by severity), serious adverse events, and adverse events causing withdrawal from the study. Patient listings of serious adverse events and adverse events leading to withdrawal will be presented.

Observed values and changes from day 1 in laboratory results and vital signs will be summarized descriptively.

Observed values in ECG parameters will be summarized, and counts and percentages of abnormal findings will be presented. Changes from baseline of the parent study in ECG parameters will be summarized descriptively. In addition, the number and percentage of patients with on-treatment QTcF values >450, >480, or >500 msec and change from day 1 >30 or >60 msec will be presented.

The use of concomitant medications will be summarized by therapeutic class using descriptive statistics. Concomitant medications will include all medications taken while the patient is treated with TEV-50717.

The frequency and severity of suicidal ideation or behavior according to the children's C-SSRS questionnaire will be presented by visit. A shift table for children's C-SSRS categories at day 1, compared to the worst (highest) category during the treatment period, will be presented.

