## 4. Procedures After TEV-50717 Treatment (Follow-Up)

### a. In-clinic Visit (Week 54)

The following procedures/assessments will be performed at week 54:

- measure vital signs (pulse, BP, body temperature, and respiratory rate)
- measure weight (Note: Weight must be measured with shoes and outerwear off.)
- perform neurological examination

- perform 12-lead ECG (after at least 5-minute rest in a supine or semi-supine position)
- perform clinical laboratory tests (serum chemistry, hematology, and urinalysis)
- perform urine pregnancy ( $\beta$ -HCG) test in females who are postmenarchal or  $\geq 12$  years of age
- administer the following questionnaires:
  - MD-CRS part I (centrally read)
  - MD-CRS part II (centrally read)
  - MD-CRS part I (physician rated, video recording)
  - MD-CRS part II (physician rated, video recording)
  - CaGI-I (to be assessed before all other investigator-rated scales during these visits)
  - CGI-I (Note: Children 13 years of age and under must be interviewed in conjunction with the caregiver. For children over 13 years of age, caregiver/adult involvement is strongly encouraged. Questions should be directed to the child, but the caregiver should be encouraged to add relevant information.)
  - CGI-S (Note: Children 13 years of age and under must be interviewed in conjunction with the caregiver. For children over 13 years of age, caregiver involvement is strongly encouraged. Questions should be directed to the child, but the caregiver should be encouraged to add relevant information.)
  - UHDRS-TMC (centrally read)
  - UHDRS-TMD (centrally read)
  - C-SSRS (Note: Children 13 years of age and under must be interviewed in conjunction with the caregiver. For children over 13 years of age, caregiver involvement is strongly encouraged. Questions should be directed to the child, but the caregiver should be encouraged to add relevant information. C-SSRS questionnaire will only be presented to patients aged  $\geq 12$  years.)
  - ESRS subscales I and II
  - CBCL (Syndrome Scale part only)
  - ESS
- inquire about adverse events
- review concomitant medications

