The titration scheme and maximum dose will be determined by body weight at day 1 and cytochrome P450 2D6 (CYP2D6) impairment status. Patients will be classified as CYP2D6 impaired if they are receiving a strong CYP2D6 inhibitor. Patients who are CYP2D6 impaired will have a dose cap in the open-label study. Safety evaluations during the titration period include assessment of vital signs, monitoring for adverse events and concomitant medications, 12-lead electrocardiograms (ECG)s, identifying patients at risk for suicide, assessment of drug-induced parkinsonism according to the Extrapyramidal Symptom Rating Scale (ESRS) subscales I and II, assessment of change in behavior according to the Child Behavior Checklist (CBCL) questionnaire, and assessment of sedation according to the Epworth Sleepiness Scale (ESS) questionnaire.

In-person (in-clinic) study visits will be scheduled at weeks 3 and 7, and telephone contacts (with non-recording live video) will be scheduled for weeks 1, 2, 4, 5, and 6 in order to assess dyskinesia and adverse events.

Maintenance period (46 weeks): At the end of the titration period (week 7), the patient's initial dose for the maintenance period (up to week 53) will be established. Dose adjustments of TEV-50717 (upward or downward) may be made during the maintenance period, if necessary, based on efficacy, safety, and/or tolerability considerations but not more often than every 5 days and only in increments of 6 mg up to the maximum allowed dose (see [Table 6](#) and [Table 7](#)).

[figure not shown]
During the maintenance period, in-person (in-clinic) study visits will be scheduled at weeks 14, 27, 40, and 53 for assessments of safety and efficacy, and telephone contacts (with non-recording live video) will be scheduled for weeks 21, 33, and 46 in order to assess adverse events and dyskinesia. At week 53/early termination (ET), patients will undergo a complete evaluation.

Washout and follow-up period: All patients should continue their usual treatment regimen up to week 53 visit (ie, the last dose can be administered until visit completion, if applicable). No dosing will be given after the week 53 visit. All patients will discontinue TEV-50717 at the week 53 visit and will return 1 week later (week 54) for evaluation of safety. Patients will have a follow-up telephone contact (no live video streaming) for safety evaluation 1 week after the end of the washout period (2 weeks after their last dose of TEV-50717) (week 55).

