8.8. Vital Signs

Vital signs (blood pressure [BP; systolic/diastolic], respiratory rate, body temperature, and pulse) will be measured at the time points detailed in [Table 2](#) and [Table 3](#).

Vital signs values and changes from baseline to each visit will be summarized using descriptive statistics.

Orthostatic systolic and diastolic BP and pulse will be calculated as supine or semi erect/seated measurement minus standing measurement and values and changes from baseline to each visit will be summarized using descriptive statistics.

Orthostatic hypotension (determined by BP measurements only; positive value in case of abnormality) is defined as having either a ≥ 20 mmHg reduction from supine to standing position in systolic blood pressure (SBP) or ≥ 10 mmHg reduction from supine to standing position in diastolic blood pressure (DBP) or both. Orthostatic tachycardia is defined as pulse increase ≥ 20 bpm from supine to standing position.

Summaries of potentially clinically significant abnormal values will include all post-baseline values (including scheduled, unscheduled, and withdrawal visits). The incidence of potentially clinically significant abnormal values will be summarized using descriptive statistics with the criteria specified in [Table 8](#).

[Table 8](#) specifies the criteria for identifying vital signs as potentially clinically significant abnormal values.

Table 8: Criteria for Potentially Clinically Significant Vital Signs

Vital Sign (unit)	Age	Potentially Clinically Significant Low Criterion value	Potentially Clinically Significant High Criterion value
SBP (supine) (mmHg)	6-12	Value ≤ 70 and ≥ 20 decrease from baseline	Value ≥ 120 and ≥ 20 increase from baseline
	13-18	Value ≤ 90 and ≥ 20 decrease from baseline	Value ≥ 135 and ≥ 20 increase from baseline
DBP (supine) (mmHg)	6-12	Value ≤ 40 and ≥ 15 decrease from baseline	Value ≥ 80 and ≥ 15 increase from baseline
	13-18	Value ≤ 50 and ≥ 15 decrease from baseline	Value ≥ 90 and ≥ 15 increase from baseline
Pulse rate (supine) (bpm)	6-10	Value ≤ 60 and ≥ 15 decrease from baseline	Value ≥ 135 and ≥ 15 increase from baseline
	11-18	Value ≤ 50 and ≥ 15 decrease from baseline	Value ≥ 120 and ≥ 15 increase from baseline
SBP orthostatic criteria (mmHg)	~	≥ 20 decrease from supine to standing position	NA
DBP orthostatic criteria (mmHg)	~	≥ 10 decrease from supine to standing position	NA
Pulse rate orthostatic criteria (bpm)	~	NA	≥ 20 increase from supine to standing position

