Shifts (normal and abnormal) from baseline to overall result interpretation and each visit will be summarized using patient counts for the centrally-read interpretation. For overall result interpretation the worst post-baseline finding for the patient (the abnormal finding if there are both normal and abnormal findings) will be used in the summaries. Summary statistics for ECG variables values will be presented. Actual values and changes from baseline to each visit will be summarized using descriptive statistics.

QTcF values will be classified as having QTc prolongation if any of the following conditions are met.

- Confirmed QTcF >450 msec
- Confirmed QTcF >480 msec
- Confirmed QTcF >500 msec
- Increase from baseline QTcF > 60 msec
- Increase from baseline confirmed QTcF > 60 msec

The confirmed QTcF is defined as the average of up to 3 standard ECG values at a visit, or a single summary ECG. If there are more than 3 standard or more than one summary ECG at a visit, then use the last ECGs for the confirmed QTcF.

The number and percentage of patients with QTc prolongation will be summarized overall, and by visit.

The incidence of potentially clinically significant abnormal values for ECG variables will be summarized using descriptive statistics with the criteria presented in [Table 9](#). The summary will be completed by age groups (6 to < 8 years, 8 to < 12 years, 12 to < 16 years, and ≥ 16 years), and overall.

Table 9: Potentially Clinically Significant Values for ECG Variables by Age

ECG parameter (unit) ^a	Age (years old)	Potentially Clinically Significant Low	Potentially Clinically Significant High
Heart Rate (bpm)	6 to <8	< 65	> 115
	8 to <12	< 55	> 110
	12 to <16	< 50	> 105
	≥ 16	< 50	> 100
PR interval (msec)	6 to <8	--	> 160
	8 to <12	--	> 175
	12 to <16	--	> 180
	≥ 16	--	> 200
QRS interval (msec)	6 to <8	--	> 100
	8 to <12	--	> 105
	12 to <16	--	> 110
	≥ 16	--	> 120

^a bpm=beats per minute; HR=heart rate; PR interval =Time from the beginning of the P wave to the beginning of the QRS complex in electrocardiogram; RR interval =Time between the start of one R wave and the start of the next R wave in the ECG; QRS duration =Graphical deflections corresponding to ventricular depolarization in a typical electrocardiogram

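### The protocol promises on-treatment QTcF counts, but SAP 8.9 puts no on-treatment limit on its overall count, so the week 54 ECG, taken off drug, enters it

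*SAP*

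**What the plan says.** **Protocol.** Section 9.6, and the safety analysis text of the synopsis, promise patient counts for "on-treatment QTcF values >450, >480, or >500 msec and change from day 1 >30 or >60 msec will be presented". The words on-treatment are attached to QTcF only. For other ECG findings the protocol promises counts of abnormal results, and for vital signs it promises abnormal values on predefined criteria. Neither has a time limit.

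**SAP 8.9.** This section lists the QTc prolongation categories (confirmed values above 450, 480 and 500 msec, and increases above 60 msec) and then says: "The number and percentage of patients with QTc prolongation will be summarized overall, and by visit". It does not mention treatment. The shift table of ECG interpretation works on a similar basis: "For overall result interpretation the worst post-baseline finding for the patient".

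**SAP 8.1 and 8.8.** The general rule for potentially clinically significant (PCS) values is "Summaries of potentially clinically significant abnormal values will include all post-baseline values (including scheduled, unscheduled, and early termination visits". Section 8.8 repeats it for vital signs: "Summaries of potentially clinically significant abnormal values will include all post-baseline values (including scheduled, unscheduled, and withdrawal visits".

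**Design.** SAP 2.1: "All patients will discontinue TEV-50717 at the week 53 visit and will return 1 week later (week 54) for evaluation of safety". The schedule tables and protocol Appendix C place a 12-lead ECG and vital signs at week 54.

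**Status of differences.** The SAP introduction says the SAP is meant to agree with the protocol and prevails where the two differ. SAP Section 11, on changes from the protocol, reads not applicable.

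**The concern.** Every completer has an ECG a week after stopping drug. SAP 8.9 gives a programmer no reason to leave that ECG out of the overall QTc count. A patient whose QTcF is unremarkable at every on-drug visit, and who crosses a threshold only at week 54, would be reported in the row that stands where the protocol promised an on-treatment count.

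ECG parameters are among the measures for the primary objective. The study has one arm of about 45 patients, so no comparator would absorb the difference. The count delivered would not be the count promised, and nothing in the SAP declares the change.

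**Working it through.** **1. Is week 54 off drug?** The schedule puts week 53 on day 371 and week 54 on day 378: 378 − 371 = 7 days. Scheduled post-baseline ECGs fall at weeks 3, 7, 14, 27, 40, 53 and 54. Six are on drug and one is off, so 1/7 = 14% of scheduled ECG visits are off drug. SAP 4.4 ends the Overall Treatment Period at the week 53 visit or, for early stoppers, at the later of last dose and the early termination visit. Week 54 is therefore in the SAP's own Follow-up Period.

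**2. The texts side by side.**

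| Output | Protocol 9.6 | SAP | Conflict? |
|---|---|---|---|
| QTcF threshold counts | On-treatment | Overall and by visit, no limit (8.9) | Yes |
| Worst-finding ECG shift | Abnormal findings, no limit | Worst post-baseline (8.9) | No |
| PCS heart rate, PR, QRS (SAP Table 9) | No on-treatment limit | All post-baseline (8.1) | No |
| PCS vital signs (SAP Table 8) | Predefined criteria, no limit | All post-baseline (8.1, 8.8) | No |

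The rule in 8.1 governs PCS values, and QTcF is not in Table 9. The rule therefore does not define the QTcF count. It only shows which way an unrestricted count is likely to be programmed.

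**3. Direction.** Patients flagged over seven visits include all those flagged over six. The overall count is therefore equal to or above the on-treatment count, never below it.

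**4. Can the by-visit rows recover the promised figure?** No. The week 54 row counts patients flagged at week 54, including those already flagged on drug. Subtracting it from the overall count gives at best a lower bound.

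**5. Size (illustration only).** The plan states no figure to reproduce and gives no per-visit rate, so *p* is assumed. It is also assumed that all 45 reach week 54 and that *p* is the same on and off drug.

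*Independent visits.* Incidence over *k* visits is 1 − (1 − p)^k.

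| p | 6 visits | 7 visits | Extra of 45 |
|---|---|---|---|
| 0.5% | 2.96% | 3.45% | 0.22 |
| 1% | 5.85% | 6.79% | 0.42 |
| 2% | 11.42% | 13.19% | 0.80 |
| 5% | 26.49% | 30.17% | 1.65 |
| 10% | 46.86% | 52.17% | 2.39 |

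For example, at 2%: 45 × (0.1319 − 0.1142) = 0.80.

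*Correlated visits.* QTcF values within a patient are related, so independence overstates the excess. With an equicorrelated latent normal variable of correlation ρ and cut-off t = Φ⁻¹(1 − p), incidence over *k* visits is 1 − ∫ φ(z) Φ((t − √ρ·z)/√(1 − ρ))^k dz. For ρ from 0.7 down to 0.3, the extra patients among 45 are:

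- p = 0.5%: 0.09 to 0.18
- p = 1%: 0.16 to 0.34
- p = 2%: 0.27 to 0.59
- p = 5%: 0.5 to 1.1, reaching one patient only at ρ of about 0.3 or less

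For scale, one patient of 45 is 2.2 percentage points.

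**The case against.** **The SAP is silent; it does not contradict the protocol.** Section 8.9 never says all post-baseline values for QTc, and the SAP is intended to agree with the protocol. The on-treatment limit could be read as still in force. This partly stands: the problem is an omission. But SAP 4.4 defines treatment and follow-up periods that 8.9 does not use. SAP 8.11 limits the suicidality shift table to the worst category in the treatment period, so the SAP states such a limit elsewhere. Silence in 8.9 leaves the programmer to choose, and the nearest general rule points to including week 54.

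**Counting washout values is a legitimate safety choice.** Week 54 exists to evaluate safety, and adverse events are collected for two weeks after last dose. This stands as an argument for showing week 54. It does not justify dropping the promised QTcF restriction without recording it.

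**Stronger readings that the documents do not support.**

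- A reader might infer that all vital-sign and ECG abnormality tables misreport off-drug values as incidence on TEV-50717. The protocol sets no on-treatment limit for them, the SAP says openly that PCS summaries use all post-baseline values, and no table is labelled as on drug. The orthostatic criteria are scheduled after baseline only at weeks 14 and 53 or early termination.
- A reader might infer that the plan hides when a QTc abnormality occurred. QTc counts and ECG shifts are also given by visit, so week 54 can be seen there. What is missing is the patient-level on-treatment total.
- A reader might infer about one extra patient per parameter. With correlated visits that needs roughly 5% per visit and low correlation. Early stoppers have a telephone follow-up and no scheduled week 54 ECG, so fewer than 45 may contribute.

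**Conclusion.** The point holds for QTcF. Protocol 9.6 and the synopsis promise an on-treatment count. SAP 8.9 as written yields an overall count that can include an ECG taken a week off drug, and Section 11 does not declare the difference. As an on-treatment figure the count is equal or too high, and the by-visit rows do not repair it.

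The likely effect is small: at 2% per visit, 0.27 to 0.59 of 45 patients with within-patient correlation 0.3 to 0.7, and 0.80 if visits were independent. These figures rest on assumed rates, all 45 patients reaching week 54, and the same chance of crossing a limit on and off drug. The reason to act is that protocol and SAP should define the same primary-objective safety count, and settling this is easy.

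The PCS vital-sign table, the PCS heart rate, PR and QRS table, and the worst-finding ECG shift do not conflict with the protocol.

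**What to change.** In SAP 8.9, base the overall QTcF threshold and change-from-baseline counts on the Overall Treatment Period of SAP 4.4. Show week 54 and any later values in a separate Follow-up Period row.

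Use that period and not a plain cut-off at last dose. Early termination visits take place as soon as possible after last dose, so a last-dose cut-off would move those ECGs out of the headline row, including those of patients who stopped for an adverse event. SAP 4.4 keeps them in.

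If the sponsor prefers an unrestricted overall count, Section 11 should record that as a departure from protocol 9.6. The same edit can settle the increase above 30 msec, which the protocol promises and the 8.9 list omits.

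For the PCS tables and the worst-finding shift, a treatment/follow-up split is an optional extra row, with the all-post-baseline row kept.

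The cost is a sentence or two in the SAP and one table row. Washout abnormalities leave the QTcF headline row but stay visible in their own row.

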8.2. Duration of Exposure to Study Drug

Duration of exposure to study drug (days) for individual patients is the number of days patient received drug (last day of study drug – first day of study drug + 1). Duration of treatment (days) will be summarized using descriptive statistics. Weeks on treatment using the categories ≤ 4 weeks, >4 to ≤ 7 weeks, >7 to ≤ 21 weeks, >21 to ≤ 27 weeks, >27 to ≤ 33 , >33 to ≤ 40 , >40 to ≤ 46 , >46 to ≤ 53 , and >53 weeks will also be summarized using descriptive statistics.

8.3. Adverse Events

Adverse events will be collected and recorded from the time a patient signs the informed consent to the end of follow-up period. For this study, the follow-up period for recording of adverse events is defined as 2 weeks after the last dose of TEV-50717.

All adverse events will be coded using MedDRA. Each patient will be counted only once in each preferred term or SOC category for the analyses of safety. Unless otherwise specified, adverse events will be summarized by SOC and preferred term, with SOCs and preferred terms within SOCs presented in descending order of patient incidence. Summaries will be presented for all adverse events (overall and by severity), adverse events determined by the investigator to be related to test IMP (ie, reasonable possibility; see Table 9 of the study protocol - defined as related or with missing relationship), overall and by severity, serious adverse events, and adverse events causing withdrawal from the study. Most common adverse events, defined as occurring in $> 4\%$ of the patients in overall, and by preferred term. Summaries will be presented by all patients.

Summaries will include treatment-emergent adverse events which are defined as adverse events occurring at or after the first dose of the IMP. The listings will include all adverse events recorded.

Patient listings of all adverse events, serious adverse events, adverse events leading to study drug discontinuation, adverse events leading to dose interruption and adverse events leading to death will be presented.

8.4. Deaths

If any patient dies during the study, a listing of deaths will be provided, and all relevant information will be discussed in the patient narrative included in the CSR.

8.5. Clinical Laboratory Tests

Summary statistics for chemistry, hematology and coagulation, and urinalysis laboratory tests are assessed at screening and weeks 3, 7, 14, 27, 40, 53/ET, and 54/follow-up visits. Laboratory values and changes from baseline to week 53 will be presented.

A list of laboratory tests is included in Table 10 of the study protocol.

Shifts (below, within, and above the normal range) from baseline to each visit will be summarized using patient counts for all the laboratory tests as applicable. Only patients with both baseline and post-baseline assessments will be summarized in the shift tables.

Only central laboratory assessments will be summarized; local laboratory assessments will be listed. Values below the lower limit of quantification or above the upper limit of quantification will be assessed on a case-by-case basis if present in the data and discussed in the final blinded statistical data review meeting.

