Assessment of drug-induced parkinsonism according to the ESR (subscale I and II), assessment of change in behavior according to the CBCL questionnaire, and assessment of sedation according to the ESS questionnaire will be summarized descriptively.

Safety assessments and time points are provided in [Table 5](#).

For continuous variables, descriptive statistics will be provided for actual values and changes from day 1 to each time point. For categorical variables, patient counts and percentages will be provided. Descriptive summaries of serious adverse events, patient withdrawals due to adverse events, and potentially clinically significant abnormal values (clinical laboratory or vital signs) based on predefined criteria will be provided as well.

If any patient dies during the study, a listing of deaths will be provided and all relevant information will be discussed in the patient narrative included in the CSR.

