4.4. Study Days and Visits

Study days will be numbered relative to the baseline visit date. Day 1 is defined as the date of the baseline visit, and the first dose of the IMP will be taken the next morning (day 2). Days will be numbered relative to baseline (ie, ..., -2, -1, 1, 2, ...; day -1 being the day before the baseline visit).

For efficacy and safety by-visit analyses, data collected at post-baseline scheduled visits will be included using their scheduled visit.

Data collected at early termination and unscheduled visits will be included and assigned to a visit window as described below.

Table 4: Visit Windows for Early Termination Visit for Efficacy Assessments

Assessment ^a	Study Day Window	Scheduled Day	Scheduled Visit/Week
MD-CRS, CaGI-I, CGI-S	Day 2 - 143	Day 98	Week 14
	Day 144 - 234	Day 189	Week 27
	Day 235 - 325	Day 280	Week 40
	Day 326 - 374	Day 371	Week 53
	≥Day 375	Day 378	Week 54
UHDRS-TMS, UHDRS-TMC, UHDRS-TMD	Day 2 - 143	Day 98	Week 14
	Day 144 - 234	Day 189	Week 27
	Day 235 - 325	Day 280	Week 40
	≥Day 326	Day 371	Week 53
PEDI-CAT, COPM	Day 2 - 280	Day 189	Week 27
	≥Day 281	Day 371	Week 53

Statistical Analysis Plan

Uncontrolled Study—Dyskinesia in Cerebral Palsy

Study TV50717-CNS-30081

Assessment ^a	Study Day Window	Scheduled Day	Scheduled Visit/Week
CGI-I	Day 2 – 10	Day 7	Week 1
	Day 11 – 17	Day 14	Week 2
	Day 18 – 24	Day 21	Week 3
	Day 25 – 31	Day 28	Week 4
	Day 32 – 38	Day 35	Week 5
	Day 39 – 45	Day 42	Week 6
	Day 46 – 73	Day 49	Week 7
	Day 74 – 122	Day 98	Week 14
	Day 123 – 168	Day 147	Week 21
	Day 169 – 210	Day 189	Week 27
	Day 211 – 255	Day 231	Week 33
	Day 256 – 301	Day 280	Week 40
	Day 302 – 346	Day 322	Week 46
	Day 347 – 374	Day 371	Week 53
	Day 375 – 381	Day 378	Week 54
	≥Day 382	Day 385	Week 55

^aMD-CRS=Movement Disorder-Childhood Rating Scale; CaGI-I=Caregiver Global Impression of Improvement; CGI-I=Clinical Global Impression of Improvement; CGI-S=Clinical Global Impression of Severity; UHDRS-TMS=Unified Huntington's Disease Rating Scale—Total Motor Score; UHDRS-TMC=Unified Huntington's Disease Rating Scale—Total Maximal Chorea; UHDRS-TMD=Unified Huntington's Disease Rating Scale—Total Maximal Dystonia; PEDI-CAT=Pediatric Evaluation Disability Inventory—Computer Adapted Test; COPM=Canadian Occupational Performance Measure;

Table 5: Visit Windows for Early Termination Visit for Safety Assessments

Assessment ^a	Study Day Window	Scheduled Day	Scheduled Visit/Week

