Vital signs and weight, 12-Lead ECG, C-SSRS, ESRS, CBCL-Syndrome Scale, ESS, Chemistry/hematology/urinalysis	Day 2 – 35	Day 21	Week 3
	Day 36 – 73	Day 49	Week 7
	Day 74 – 143	Day 98	Week 14
	Day 144 – 234	Day 189	Week 27
	Day 235 – 325	Day 280	Week 40
	Day 326 – 374	Day 371	Week 53
	≥Day 375	Day 378	Week 54
Physical examination, Height	Day 2 – 280	Day 189	Week 27
	≥Day 281	Day 371	Week 53

Assessment ^a	Study Day Window	Scheduled Day	Scheduled Visit/Week
Orthostatic Vital Signs	Day 2 – 234	Day 98	Week 14
	>Day 235	Day 371	Week 53
Neurological examination	Day 2 – 374	Day 371	Week 53
	≥Day 375	Day 378	Week 54
CBCL-full assessment	≥Day 2	Day 371	Week 53

^a CBCL=Child Behavior Checklist (for ages 6-18); C-SSRS=Columbia-Suicide Severity Rating Scale; ECG=electrocardiogram; ESRS=Extrapyramidal Symptom Rating Scale (subscale I and II); ESS =Epworth Sleepiness Scale (for children and adolescents);

After mapping the data to the analysis visits of unscheduled and early termination visits, the following rules will apply unless other handling is specified for a particular analysis:

- If there is a scheduled visit in the analysis window, the last non-missing scheduled visit will be selected.
- If there is no scheduled visit, but early termination visit, early termination visit will be selected.
- If there are no scheduled or early termination visits, the record closest to the planned assessment day will be selected for analysis.
- If there are no scheduled or early termination visits, and 2 records are equidistant from the scheduled day, then the later record will be selected.
- If a patient has no scheduled record or early termination/unscheduled visits in an analysis window, the patient will be considered missing at that visit.

For these analyses performed by time period, eg, adverse events, the following definitions will be used:

- Titration Period - from the first dose of treatment until the day of the week 7 visit. For patients discontinued before the week 7, the Titration Period is until the later of the last dose of treatment and the early termination visit.
- Maintenance Period - from the day after the week 7 visit until the day of the week 53 visit. If a patient enters the Maintenance Period but discontinues treatment early, the Maintenance Period is until the later of the last dose of treatment and the early termination visit.
- Overall Treatment Period - includes the Titration and the Maintenance Periods, if applicable.

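### A scheduled laboratory result displaces any unscheduled or early-termination result in its window, and SAP 8.5 has no worst-value or clinically-significant-value table to catch what is dropped

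*SAP*

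**What the plan says.** SAP 8.5 names three laboratory outputs. The first two are values and change: "Laboratory values and changes from baseline to week 53 will be presented". The third is normal-range shifts, "from baseline to each visit will be summarized using patient counts for all the laboratory tests as applicable".

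SAP 4.4 sets how a record is chosen for a by-visit table. ET and unscheduled results are not discarded at the outset: "Data collected at early termination and unscheduled visits will be included and assigned to a visit window as described below". They are then ranked. First, "If there is a scheduled visit in the analysis window, the last non-missing scheduled visit will be selected". Next, "If there is no scheduled visit, but early termination visit, early termination visit will be selected". Only if neither exists is the unscheduled record closest to the planned day used. SAP Table 5 gives the windows and names chemistry, hematology and urinalysis.

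SAP 8.1 sets two general rules for safety data. For continuous variables, "descriptive statistics will be provided for actual values and changes from baseline to each time point". For PCS values, "Summaries of potentially clinically significant abnormal values will include all post-baseline values (including scheduled, unscheduled, and early termination visits".

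Protocol 9.6 has the same rule for continuous variables: "For continuous variables, descriptive statistics will be provided for actual values and changes from day 1 to each time point". It also promises descriptive summaries of PCS values for laboratory tests and vital signs, on criteria fixed in advance. SAP Section 11 records no change from the protocol's analyses.

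**The concern.** Unscheduled laboratory tests are drawn at the investigator's discretion, typically because something needs checking, and ET tests are drawn when a patient stops. These are the results most likely to be abnormal, yet they give way to a scheduled result in the same window. A transient abnormality that has resolved by the scheduled visit, or that appears after it in the same window, is then tabulated as within range.

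Safety is the primary objective and laboratory parameters are a named endpoint. The laboratory tables could therefore look clean while the individual data are not, and a reader of the tables could not tell.

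**Working it through.** **Inputs.** Laboratory windows and planned days from SAP Table 5; selection order from SAP 4.4; last planned study day, 385 (week 55), from SAP Table 3. The plan gives no figure of its own to reproduce.

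**Step 1: windows.** Width = last day − first day + 1. The open-ended last window is cut at day 385.

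| Visit | Window (days) | Width |
|---|---|---|
| Week 3 | 2–35 | 34 |
| Week 7 | 36–73 | 38 |
| Week 14 | 74–143 | 70 |
| Week 27 | 144–234 | 91 |
| Week 40 | 235–325 | 91 |
| Week 53 | 326–374 | 49 |
| Week 54 | 375–385 | 11 |

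Each window starts the day after the previous one ends. The widths add up: 34 + 38 + 70 + 91 + 91 + 49 + 11 = 384 = 385 − 2 + 1. No day lies outside a window.

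**Step 2: all seven scheduled laboratory visits done.** One abnormal unscheduled result was placed on each day from 2 to 385 in turn and the selection order applied. It was selected on 0 of 384 days. Small departures from the planned visit day do not alter this, because SAP 4.4 keeps scheduled data at their scheduled visit.

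**Step 3: one scheduled visit missing, no ET result in that window.** The unscheduled result is now selected on every day of that window: 34, 38, 70, 91, 91, 49 or 11 days, as in the table. The displacement therefore depends on a scheduled result being present.

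**Step 4: an ET result.** Suppose the week 27 tests are normal on day 189, and the patient stops with abnormal ET tests on day 200. Both days lie in 144–234, so the normal scheduled result is tabulated. The ET result does not become the week 53 value either, because ET data are mapped by study day and week 53 covers days 326–374.

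**Step 5: is there another table that would catch the value?**
- PCS table: SAP 8.1 would admit unscheduled and ET results, and protocol 9.6 promises such a summary for laboratory tests. The SAP sets PCS criteria for vital signs (Table 8) and ECG (Table 9), and none for laboratory tests. The general rule has nothing to act on.
- Worst-value shift: SAP 8.9 uses the worst post-baseline finding for the ECG interpretation, and SAP 8.11 uses the worst category on treatment for the C-SSRS. SAP 8.5 has no counterpart.
- Adverse events: protocol 7.5 records a clinically significant result as an adverse event. This is the one remaining route to a summary.

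**Step 6: what one patient is worth.** With about 45 patients, one hidden abnormality changes an incidence by 1/45 = 2.2 percentage points.

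**The case against.** The strongest reply is that the SAP does not ignore unscheduled data. A reader might infer that only scheduled records are used, or that an unscheduled value can never reach a laboratory table. SAP 4.4 does not support that: its order runs from scheduled to ET to unscheduled, and Step 3 shows the fallback working. Missing scheduled tests are also foreseeable, since protocol Appendix M makes weeks 3 and 14 optional in an emergency.

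A reader might also take the week 53 wording in SAP 8.5 as proof that titration changes and early stoppers are left out. It is not. SAP 8.1 calls for change to each time point, SAP 8.5 itself lists weeks 3 to 54, and its shifts go to each visit. This is an inconsistency to settle, not a demonstrated omission.

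Nor is the ECG the only place where the SAP looks at the worst value, since the C-SSRS shift does so too.

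The adverse event route is wider than investigator opinion. Protocol 7.1.1 counts an abnormality that leads to withdrawal, treatment or further work-up, and protocol 5.8 requires the reason for a suspension to be documented in the related adverse event form. An abnormality that causes a suspension or withdrawal should therefore appear among the adverse events. That reduces the risk of losing an event altogether, but an adverse event term does not show the analyte's shift or how far it moved.

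Finally, neither document promises a worst-value shift for laboratory tests, and the study is small and descriptive. That is fair for the shift table. It does not answer the missing laboratory PCS summary, which protocol 9.6 does promise.

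**Conclusion.** The point holds in a conditional form. Where a window contains a scheduled laboratory result, any unscheduled or ET result in it is excluded from the by-visit value, change and shift tables. For a patient with complete scheduled laboratory visits, that means every unscheduled result (0 of 384 days selected). SAP 8.5 provides no worst-value shift and no laboratory PCS criteria or table. The second gap departs from protocol 9.6 and is not declared in SAP Section 11.

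This assumes that the SAP 4.4 order governs the laboratory value, change and shift tables, as the naming of laboratory tests in Table 5 indicates, and that the results are central ones. Local results are only listed under SAP 8.5. The number of patients affected cannot be estimated, because the documents give no rate of unscheduled draws or of abnormal results. The change is worth making before database lock because it concerns a primary safety endpoint and costs little.

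**What to change.** Amend SAP 8.5 as follows.

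1. For each analyte, add a shift from baseline to the lowest and to the highest value in the overall treatment period defined in SAP 4.4. Use all central results: scheduled, unscheduled and ET. Keep the by-visit shifts.
2. Define laboratory PCS criteria in advance, with an incidence table over all post-baseline values, as protocol 9.6 promises and SAP 8.1 assumes. If this is not intended, declare the omission and the reason in Section 11.
3. Present change from baseline at every scheduled visit, so that SAP 8.5 agrees with SAP 8.1 and protocol 9.6.

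The cost is one or two extra tables per laboratory panel and the work of agreeing PCS limits. No new data are needed.
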